### **2.6.2 Overview of analysis methods of efficacy variables**

An overview of statistical analyses and methods applied to psoriasis efficacy variables is given in [Table 2-10](#).

**Table 2-10 Overview of analysis methods for efficacy variables**

| Variable(s)  | Summary statistics for binary/ categorical data | Exact Logistic regression | Summary Statistics for continuous data | Time-to-event analysis | Graphs |
|--|---|---------------------------|--|------------------------|--------|
| PASI 75 at Week 12, compared to Placebo                      | X   | X                         |  |                        | X      |
| IGA mod 2011 0 or 1 response at Week 12, compared to Placebo | X   | X                         |  |                        | X      |
| PASI 90 response at Week 12, compared to Placebo             | X   | X                         |  |                        | X      |

| Variable(s)   | Summary statistics for binary/ categorical data | Exact Logistic regression | Summary Statistics for continuous data | Time-to-event analysis | Graphs |
|---|---|---------------------------|--|------------------------|--------|
| PASI 50/75/90/100 response over time                    | X   | X                         |  |                        | X      |
| IGA mod 2011 0 or 1 response over time                  | X   | X                         |  |                        | X      |
| PASI score over time, compared to Placebo               |   |                           | X                                      |                        | X      |
| IGA mod 2011 score over time, compared to Placebo       | X   |                           |  |                        |        |
| Change in CDLQI over time up to Week 52                 |   |                           | X                                      |                        |        |
| CDLQI 0 or 1 achievement over time, compared to Placebo | X   |                           |  |                        | X      |
| CHAQ score over time                                    |   |                           | X                                      |                        |        |
| CHAQ response over time                                 | X   |                           |  |                        |        |
|   |   |                           |  |                        |        |

### 2.6.3 Statistical hypothesis, model, and method of analysis

The statistical hypotheses for PASI 75 response at Week 12 and IGA mod 2011 0 or 1 response at Week 12 being tested is that secukinumab (low or high dose) is not superior to placebo in the proportion of subjects with PASI 75 and IGA mod 2011 0 or 1 response at Week 12.

Let  $p_j$  denote the proportion of PASI 75 responders at Week 12 for treatment group  $j$  and  $r_j$  denote the proportion of IGA 0 or 1 responders at Week 12 for treatment group  $j$ ,  $j=0, 1, 2$ ,

where

- 0 corresponds to placebo,
- 1 corresponds to secukinumab low dose,
- 2 corresponds to secukinumab high dose.

The following hypotheses will be tested

$H_1: p_1 - p_0 \leq 0$  versus  $H_{A1}: p_1 - p_0 > 0$ ,

$H_2: p_2 - p_0 \leq 0$  versus  $H_{A2}: p_2 - p_0 > 0$ ,

$H_3: r_1 - r_0 \leq 0$  versus  $H_{A3}: r_1 - r_0 > 0$ ,

$H_4: r_2 - r_0 \leq 0$  versus  $H_{A4}: r_2 - r_0 > 0$ .

In other words:

$H_1$ : secukinumab low dose is not superior to placebo with respect to PASI 75 response at Week 12

$H_2$ : secukinumab high dose is not superior to placebo with respect to PASI 75 response at Week 12

$H_3$ : secukinumab low dose is not superior to placebo with respect to IGA mod 2011 0 or 1 response at Week 12

$H_4$ : secukinumab high dose is not superior to placebo with respect to IGA mod 2011 0 or 1 response at Week 12

The primary endpoint (PASI 75 and IGA mod 2011 0 or 1 response at Week 12) will be evaluated using an exact logistic regression model with treatment group, baseline body weight stratum, age stratum and baseline PASI score as explanatory variables (refer to the appendix “5.1.2.2 Exact Logistic regression” for more details).

If exact logistic regression model does not converge, then the following steps will be performed:

- If convergence not reached, remove the covariates from the model one by one until convergence is reached; start with removing continuous covariates (i.e., baseline PASI), followed by removing categorical covariates (i.e., age, bodyweight strata);
- If convergence not reached at all, then perform Fisher’s exact test.

Odds ratios will be computed for comparisons of secukinumab dose regimens versus placebo utilizing the exact logistic regression model fitted. In case of response rates of 0% or 100% in one of the treatment groups, for analyses with multiple imputation, confidence intervals for risk difference and p-values from the t-test for the risk difference comparing to 0 will be provided; for analyses with pure non-responder imputation, Fisher’s exact test will be applied and confidence intervals for risk difference will be provided.

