### **9.4.2 Statistical model, hypothesis, and method of analysis**

The statistical hypotheses for PASI 75 response at Week 12 and IGA 0 or 1 response at Week 12 being tested is that secukinumab (low or high dose) is not superior to placebo in the proportion of subjects with PASI 75 and IGA 0 or 1 response at Week 12.

Let  $p_j$  denote the proportion of PASI 75 responders at Week 12 for treatment group  $j$  and  $r_j$  denote the proportion of IGA 0 or 1 responders at Week 12 for treatment group  $j$ ,  $j=0, 1, 2$ , where

- 0 corresponds to placebo,
- 1 corresponds to secukinumab low dose,
- 2 corresponds to secukinumab high dose.

The following hypotheses will be tested

$$H_1: p_1 - p_0 \leq 0 \text{ versus } H_{A1}: p_1 - p_0 > 0,$$

$$H_2: p_2 - p_0 \leq 0 \text{ versus } H_{A2}: p_2 - p_0 > 0,$$

$$H_3: r_1 - r_0 \leq 0 \text{ versus } H_{A3}: r_1 - r_0 > 0,$$

$$H_4: r_2 - r_0 \leq 0 \text{ versus } H_{A4}: r_2 - r_0 > 0.$$

In other words:

$H_1$ : Secukinumab low dose is not superior to placebo with respect to PASI 75 response at Week 12

$H_2$ : secukinumab high dose is not superior to placebo with respect to PASI 75 response at Week 12

$H_3$ : secukinumab low dose is not superior to placebo with respect to IGA 0 or 1 response at Week 12

$H_4$ : secukinumab high dose is not superior to placebo with respect to IGA 0 or 1 response at Week 12

The primary analysis method will be the exact logistic regression with all 4 treatment groups (including etanercept); baseline bodyweight, age stratum and baseline PASI score as explanatory variables. Odds ratios will be computed for comparisons of secukinumab dose regimens versus placebo utilizing the logistic regression model fitted. Confidence intervals for risk difference will be derived based on the exact method.

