## 2.6.4 Handling of missing values/censoring/discontinuations

The following imputation methods will apply to the missing data for analysis up to Week 52 including primary W12 analysis:

- Response variables based on PASI score and IGA mod 2011 categories will be imputed with multiple imputations (MI) method as primary imputation method. Multiple imputation (MI) is a simulation based approach where missing values are replaced by multiple Bayesian draws from the conditional distribution of missing data given the observed data and covariates, creating multiple completed data sets. These completed data sets can then be analyzed using standard methods. Within this analysis, the PASI score or

IGA mod 2011 categories will be imputed and response variables will be derived based on the imputed scores. In the multiple imputation analysis, the response status will be imputed based on the individual treatment arm information.

- (Pure) Non-responder imputation will be used as a sensitivity method: Missing values with respect to response variables based on PASI score and IGA mod 2011 categories will be imputed with non-response regardless to the reason for missing data. Subjects with missing baseline or those with all post-baseline missing will be imputed with non-response.

[REDACTED]

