### 3 Sample size calculation

Approximately 160 pediatric subjects from 6 to less than 18 years of age, with 2 subgroups: 6 to less than 12 years of age, and 12 to less than 18 years of age. Stratification is planned for age (<12 years,  $\geq$ 12 years) and weight (<25kg, 25-<50kg and  $\geq$ 50kg). It will be targeted to have at least 30 subjects in the <12 years subgroup at a minimum. Enrollment of children aged 6 to less than 12 years will proceed after efficacy and safety data for approximately 80 (approximately 40 treated with AIN) enrolled adolescents (aged 12 to less than 18 years) treated for 28 weeks have been reviewed and deemed satisfactory by a Data Monitoring Committee.

Since two secukinumab dose regimens will be tested versus placebo with respect to the coprimary endpoints (PASI 75 response and IGA 0 or 1 response at Week 12), the type-I-error will be split to 1.25% one-sided for each comparison. With 40 subjects per group and assuming a response rate of 10% for PASI 75 response and IGA 0 or 1 response in the placebo group, the power to show a response rate of 65% for PASI 75 response and 45% for IGA 0 response in the secukinumab groups based on Fisher's exact test (nQuery Advisor 7.0, two group Fisher's-exact test of equal proportions) is approximately 99% for PASI 75 response and approximately 88% for IGA mod 2011 0 or 1 response. For the secondary endpoint of PASI 90 response at week 12, assuming a response rate of 8% in the placebo group, the power to show a significant difference between a secukinumab dose and placebo, assuming a response rate of 39% in the secukinumab groups based on Fisher's exact test (nQuery Advisor 7.0, two group Fisher's-exact test of equal proportions) is approximately 82% for PASI 90 response. The assumed response rates for secukinumab are based on the confirmatory efficacy in severe patients in the adult phase III program. At Week 12, PASI 75 response rates of 11% and PASI 90 response rates of 7% have been reported in the placebo group in [Paller et al \(2008\)](#) for children and adolescents aged 4-17 years.

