### 5.1.2.3 Multiple imputations for response variables

PASI 75 and IGA 0 or 1 response at Week 12 will be evaluated using an exact logistic regression model with treatment group baseline body weight stratum, age stratum and

baseline PASI as effects with multiple imputations for missing values. In addition, exact logistic regression analysis for PASI 50, PASI 75, PASI 90, PASI 100 and IGA mod 2011 0 or 1 response by visits will be analyzed using multiple imputation method.

Summary statistics for PASI 50, PASI 75, PASI 90, PASI 100, and IGA mod 2011 0 or 1 response by visit will be presented in contingency tables with multiple imputations method.

In the multiple imputations analysis, the response status will be imputed based on the individual treatment arm information.

In case of higher drop-out rates or higher study treatment discontinuations for reasons other than lack of efficacy, additional sensitivity analyses will be performed.

Multiple imputation (MI) is a simulation based approach where missing values are replaced by multiple Bayesian draws from the conditional distribution of missing data given the observed data and covariates, creating multiple completed data sets. These completed data sets can then be analyzed using standard methods. [Rubin \(1987\)](#) presented rules how to combine the multiple sets of estimates to produce overall estimates and confidence intervals that adequately incorporate missing data uncertainty.

Missing values for the 'PASI score', 'IGA mod 2011 score', 'change from baseline PASI score' and 'change from baseline IGA score' will be imputed simultaneously based on an underlying normal distribution and using a Markov Chain Monte Carlo (MCMC) method. The change from baseline in PASI score appears to follow closer to a normal distribution than the actual PASI score. Assuming normality for the 'IGA mod 2011 score' is motivated by [Schaefer \(1997\)](#), where it was shown that the multivariate normal approximation for the imputation of incomplete categorical and binary data is robust.

The imputations will be done separately for each treatment group including baseline weight, and number of previous systemic therapies as additional covariates.

The number of imputations will be set to 100, the seed for the random function will be set to 4572310 for this study. To generate the multiple imputed data sets, the SAS procedure MI can be used as follows:

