estimate=exp(ESTIMATE);
LCLMEAN=estimate*exp(-1.96*stderr);
UCLMEAN=estimate*exp(+1.96*stderr);
RUN ;
```

In case if exact logistic regression does not converge and risk difference estimates will be provided. The SAS procedure PROC FREQ for risk difference estimates will be applied as follows:

```
ODS LISTING CLOSE;
PROC FREQ DATA=<Imputed dataset> ORDER=DATA;
  TABLES <treatment group>*<response variable>/riskdiff fisher alpha=0.05;
  BY <By-variables>;
  ODS OUTPUT RiskDiffCol1=RiskDiffCol1 FishersExact=fisherexact;
RUN;

ODS LISTING;
DATA DRISK; SET RiskDiffCol1;
  WHERE control="1";
  ESTIMATE=risk;
  STDERR=ase;
  effect="Riskdiff";
```

```
IF missing(ESTIMATE) OR missing(STDERR) THEN DELETE;  
RUN;  
  
PROC SORT DATA=DRISK; BY <By-variables>; RUN;  
ODS LISTING CLOSE;  
ODS OUTPUT ParameterEstimates=results VarianceInfo=varinfo ModelInfo=Modelinfo;  
PROC MIANALYZE PARAMS=drisk;  
  by <By-variables>;  
  modeleffects Riskdiff;  
  stderr ase;  
RUN;  
  
ODS LISTING;  
DATA results2;  
  set results;  
  or=estimate*100;  
  lowercl=(LCLmean)*100;  
  uppercl=(UCLmean)*100;  
  KEEP <response variable> <By-variables> or lowercl uppercl probt;  
RUN;
```

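### When an arm has 0% or 100% response, the multiple-imputation fallback gives that arm zero variance, so its p-values are too small and its intervals too narrow, mainly in subgroups, at early visits and for PASI 100

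*SAP*

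**What the plan says.** Multiple imputation is the main missing-data method: PASI and IGA responses "will be imputed with multiple imputations (MI) method as primary imputation method" (SAP 2.6.4), and "The number of imputations will be set to 100" (SAP 5.1.2.3). The primary test is exact logistic regression.

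SAP 2.6.3 makes an exception when a treatment group is at 0% or 100%. For multiple-imputation analyses, "confidence intervals for risk difference and p-values from the t-test for the risk difference comparing to 0 will be provided". For non-responder imputation, in the same sentence, Fisher's "exact test will be applied and confidence intervals for risk difference will be provided".

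The only risk-difference code for imputed data is at the end of SAP 5.1.2.3, introduced for non-convergence of the exact model. It calls PROC FREQ with "TABLES <treatment group>*<response variable>/riskdiff fisher alpha=0.05" and no EXACT statement, and sets the standard error to `ase`. It then drops records whose estimate or standard error is missing, pools the rest in PROC MIANALYZE, and ends with "KEEP <response variable> <By-variables> or lowercl uppercl probt".

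Other places give different rules for the same or a neighbouring case:
- Protocol 9.4.2: "Confidence intervals for risk difference will be derived based on the exact method".
- SAP 5.1.2.1 and 5.1.3.4: exact limits for the risk difference.
- SAP 5.1.2.2: odds ratio and p-value replaced by a dash at 0% or 100%.
- SAP 2.6.3 and 5.1.2.2: Fisher's exact test if the model never converges.

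**The concern.** The Wald variance of a proportion is p(1-p)/n, which is zero at p = 0 and p = 1. The rule therefore applies this standard error exactly where it fails: the boundary arm is treated as if its true rate were known. If one arm is at 0% and the other at 100%, the whole standard error is zero, the t statistic is undefined and the interval has no width. The code would not catch this, because it removes missing standard errors but not zero ones.

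At stake is the credibility of reported p-values and intervals where a 0% placebo arm is likely. Week 12 PASI 75/90 and IGA responses are analysed by age and weight stratum (SAP Table 2-6), and response including PASI 100 is compared with placebo at each visit up to Week 12 (SAP 2.7.3).

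**Working it through.** **Inputs.** 40 per arm; placebo 10% (PASI 75, IGA 0/1) and 8% (PASI 90); secukinumab 65%, 45% and 39%. On the level, "the type-I-error will be split to 1.25% one-sided for each comparison" (SAP 3). The younger age group is expected to need 40-45 patients (SAP 1.1), allocated 1:1:1:1, so about 10-11 per arm.

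**The plan's own figures.** Full enumeration with Fisher's exact test at one-sided 0.0125 gives power 99.9%, 88.4% and 82.1%, against the stated 99%, 88% and 82%. They reproduce.

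**Formulas.**
- Fallback: SE = sqrt(p1(1-p1)/n + p0(1-p0)/n). With p0 = 0 the second term vanishes.
- Agresti-Caffo: replace each proportion by (x+1)/(n+2) and each n by n+2, in the difference and in its variance.
- Fisher: hypergeometric tail.

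The figures use the normal limit and no between-imputation variance, that is, nothing missing or identical imputations.

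**5/40 against 0/40.**
- Fallback: SE = sqrt(0.125 × 0.875/40) = 0.0523; z = 0.125/0.0523 = 2.39; one-sided p = 0.0084.
- Agresti-Caffo: 6/42 - 1/42 = 0.1190; SE = sqrt(0.1429 × 0.8571/42 + 0.0238 × 0.9762/42) = 0.0589; z = 2.02; p = 0.0216.
- Fisher: 0.0274.

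**One-sided p-values, placebo 0/40.**

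| Active arm | Fallback | Barnard | Agresti-Caffo | Fisher |
|---|---|---|---|---|
| 5/40 | 0.0084 | 0.0112 | 0.0216 | 0.0274 |
| 6/40 | 0.0039 | 0.0056 | 0.0107 | 0.0128 |

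**Interval width at 40 per arm**, fallback against score-based exact unconditional: 0.205 v 0.244 at 5/40; 0.308 v 0.324 at 18/40; 0.296 v 0.311 at 26/40.

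**Ten per arm, placebo 0/10.**
- 10/10: fallback SE = 0, interval 100% to 100%. Agresti-Caffo: 11/12 - 1/12 = 0.833; SE = sqrt(2 × (11/12)(1/12)/12) = 0.113; lower limit 0.833 - 1.96 × 0.113 = 0.61.
- 8/10: fallback 55% to 100% (upper limit cut at 100%); Agresti-Caffo 38% to 96%.
- 5/10: fallback p = 0.0008; Fisher 0.016.

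**How often placebo is at 0%.**
- Ten per arm, true rate 10%: 0.90^10 = 35%.
- Forty per arm: 0.90^40 = 1.5%; 0.92^40 = 3.6%; at a true 2% (an assumption), 0.98^40 = 45%.
- PASI 100 responders are a subset of PASI 90 responders, so the placebo rate for PASI 100 cannot exceed that for PASI 90, which is planned at 8%.

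**Effect on H1-H6.** I enumerated all outcomes at 40 per arm with equal true rates, using the fallback when either arm is at 0 or 40 and Fisher otherwise (standing in for the exact logistic test). The unconditional one-sided error is at most 0.92% at the 1.25% level and 1.9% at the 2.5% level. For common rates up to 30% the peak at the 1.25% level is 0.83%, where Fisher alone gives 0.15%. At 1.25% the decision differs from Fisher only at 5 or 6 responders against 0/40. Under the planning rates that has probability of about 1e-12 (PASI 75), 8e-7 (IGA 0/1) and 3e-5 (PASI 90).

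**Imputed responders.** As an illustration, assume two missing placebo subjects, each imputed as a responder with chance 0 to 10%. At 6/40 the fallback p moves from 0.0039 to 0.0058, still below Agresti-Caffo and Fisher with nothing missing.

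**The case against.** Three stronger readings are tempting, and the documents do not support them.

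*The fallback inflates the type I error of H1-H6.* If both arms truly respond at 5%, then given placebo 0/40 the fallback rejects 4.8% of the time. But that conditions on the most extreme control result, and the 1.25% level is not defined on that condition. Barnard's test, which is exact, has the same rejection region there. Unconditionally the error stays below nominal.

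*5/40 and 6/40 pass only because of the Wald error.* Barnard's test passes both, and Agresti-Caffo passes 6/40. Much of the gap to Fisher is Fisher's conservatism. What stands is that the fallback p-value is the smallest of the methods compared.

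*The SAP replaced the protocol's exact intervals without declaring it.* SAP 5.1.2.1 and 5.1.3.4 retain exact risk-difference intervals, while SAP 5.1.2.2 suppresses the p-value in the same case. These are conflicting rules, not a clean substitution.

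Other points stand as limits. The confidence intervals are not used for decisions (SAP 2.1). Non-responder imputation with Fisher's test sits beside the primary analysis as a check (SAP 2.6.3, 2.6.5). Subgroup and early-visit comparisons lie outside the testing strategy. The code is introduced for non-convergence, so its link to the 0%/100% rule is an inference, though no other such code exists. The SAP does not say whether the trigger is judged in each imputed set or overall, and imputed responders restore some variance. Too favourable does not always mean a higher lower limit: at 5/40 the fallback's lower limit is 0.0225 against 0.0245 for the score-based exact interval.

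**Conclusion.** The defect is real but limited. In the 0%/100% case the SAP's only risk-difference procedure for imputed data omits the boundary arm's uncertainty. Where little is imputed, p-values are about 1.3 times smaller than Barnard's and 3.3 times smaller than Fisher's at 5/40 against 0/40. Intervals are too narrow, and with one arm at 0% and the other at 100% they have zero width.

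The consequence lies mainly in the reporting of age and weight subgroups, early visits and PASI 100. This assumes that the 2.6.3 rule is carried to those analyses; SAP 5.1.2.2 would instead blank the p-value. For H1-H6 at 40 per arm, error control is not threatened and conclusions at the planned effects would almost never change. The figures assume little or no between-imputation variance and, for subgroups, about ten per arm.

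**What to change.** 1. In the 0%/100% fallback, compute in each imputed set a risk difference whose variance is not zero at the boundary, for example Agresti-Caffo, and pool by Rubin's rules. Take the p-value and limits from that pooled result, cut the limits at ±100%, and report the unadjusted difference as the point estimate.
2. Where nothing is missing for the comparison, use Fisher's exact p-value with the exact unconditional interval of Protocol 9.4.2 and SAP 5.1.3.4.
3. State whether the trigger is judged in each imputed set or overall, and whether it covers subgroups and all visits.
4. Reconcile SAP 2.6.3, 5.1.2.2, 5.1.2.3 and 5.1.3.4 so that one rule governs 0%/100% response and one governs non-convergence. State that the two-sided p-value from PROC MIANALYZE is converted to one-sided for H1-H6.

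The cost is a few lines of code and SAP wording. Intervals become somewhat wider and p-values slightly larger in boundary cases. Agresti-Caffo is approximate and appears in neither document, so it should be named as a choice.

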## 2.6.4 Handling of missing values/censoring/discontinuations

The following imputation methods will apply to the missing data for analysis up to Week 52 including primary W12 analysis:

- Response variables based on PASI score and IGA mod 2011 categories will be imputed with multiple imputations (MI) method as primary imputation method. Multiple imputation (MI) is a simulation based approach where missing values are replaced by multiple Bayesian draws from the conditional distribution of missing data given the observed data and covariates, creating multiple completed data sets. These completed data sets can then be analyzed using standard methods. Within this analysis, the PASI score or

IGA mod 2011 categories will be imputed and response variables will be derived based on the imputed scores. In the multiple imputation analysis, the response status will be imputed based on the individual treatment arm information.

- (Pure) Non-responder imputation will be used as a sensitivity method: Missing values with respect to response variables based on PASI score and IGA mod 2011 categories will be imputed with non-response regardless to the reason for missing data. Subjects with missing baseline or those with all post-baseline missing will be imputed with non-response.

[REDACTED]

